Protocol title:

Feasibility of using daily Humidified Nasal High-flow with Oxygen during Sleep and/or Daytime in Hypercapnic COPD patients following recent (< 12 wks.) hospitalization for AECOPD for 90 days

NCT03221387

Date: 10/06/2017

1) Abstract of the study

Humidified Nasal High-flow with Oxygen (HNHF-O2) therapy has been reported to have acute beneficial effects in patients with hypoxemic respiratory failure. HNHF-O2 may be beneficial in patients with COPD and chronic impairments in gas exchange, both hypoxemia as well as hypercapnia. HNHF-O2 may decrease work of breathing, reduce dyspnea, improve airway humidification, and potentially stabilize or reduce carbon dioxide levels. However, there is limited data showing the chronic effects of HNHF-O2 in patients with hypercapnic respiratory failure, specifically those discharged to home following hospitalization for an acute exacerbation. Data that demonstrates that HNHF-O2 is well tolerated, and stabilizes or improves gas exchange long term in patients with COPD is lacking. Similarly, data that demonstrates that this therapeutic regimen is feasible to provide to patients in the home environment are lacking. This is an open-labeled pilot study of thirty patients to determine the safety and feasibility of using the device in the outpatient management of patients with COPD.

2) Protocol Title

Feasibility of using daily Humidified Nasal High-flow with Oxygen during Sleep and/or Daytime in Hypercapnic COPD patients following recent (< 12 wks.) hospitalization for AECOPD for 90 days

3) IRB Review History

Not applicable

4) Investigator

[name]

5) Objectives

To assess the feasibility of using daily home HNHF-O2 during sleep and/or daytime in hypercapnic COPD patients following recent (< 12 weeks) hospitalization for AECOPD for 90 days.

6) Background

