current use (\leq 4 weeks of study entry) of any PAP-therapy (e.g., CPAP or NPPV); sleep apnea as follows: STOPBang scores \geq 5 or STOPBang score \geq 2 plus BMI $>$ 35 kg/m²; or Berlin questionnaire scores suggesting high likelihood of sleep apnea with increased risk of sleep-related accident (e.g., occupation as a commercial driver or pilot); or excessive daytime sleepiness (i.e., either of High (>15) score on the Epworth Sleepiness Scale or “fall asleep” accident or “near miss” accident in prior 12 months).

c) Local Number of Subjects

Thirty subjects will be accrued locally for this study.

We expect few screen failures.

d) Study-Wide Number of Subjects

If this is a multicenter study, indicate the total number of subjects to be accrued across all sites. – Not applicable.

e) Study Timelines

- Subjects will be followed for 90 days with regular telephone follow-up and clinic visits throughout.
- Subjects will be enrolled over a period of 12 months.
- The investigators will complete the data analysis approximately 18 months after the first subject is enrolled.

f) Study Endpoints

The primary endpoints of this study are the feasibility of oxygen therapy by HNHF-O2 at home over a 90-day period in terms of tolerance and hours of use. Descriptive statistics will be used to characterize the patient population in terms of demographic factors and severity of airflow obstruction. Changes in PaO₂, PaCO₂ and pH across the days will be done by analysis of variance. The effect of baseline PaCO₂ on change in PaCO₂ with HNHF-O2 therapy will be analyzed as an independent effect on change in PaCO₂ levels with HNHF-O2. Changes in respiratory rate, heart rate, blood pressure accessory muscle use will also be assessed by analysis of variance. Patient tolerance and side effects will also be measured across days of use per patient and across days in all patients as group trends. Hours of use per device log and per patient diary will be independently analyzed and compared to one another. The impact on change in exacerbation frequency and severity will be analyzed. Changes in spirometry, 6MWD, GOLD grade and class and BODE scores prior to and after 90 days of HNHF-O2 will be analyzed.

g) Procedures Involved in the Human Research

[figure not shown]
An overview of the study is provided in the figure below.

Outpatient HNHF-O2 Protocol

Version 3.0

10/06/2017

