Feasibility of using daily home HNHF-O2 during Sleep and/or Daytime in Hypercapnic COPD patients following recent (< 12 wks.) hospitalization for AECOPD for 90 days

¹ > 40 yrs. Age and Hospitalized for AECOPD; able to sign IC and willing to do tests

² vital signs, respiratory patient discomfort, Likert scale for clinical improvement, dyspnea (modified Borg Score, mMRC) ABG 5 minutes after inspiring O₂ to maintain SaO₂ >90%, spirometry, 6 MWT, questionnaires (CAT, SGRQ), set baseline diary for respiratory symptoms

³ Inquire about any problems and assess for adherence, troubleshoot

⁴ vital signs, respiratory patient discomfort, Likert scale for clinical improvement, dyspnea, side effects of HNHF-O₂, and review daily electronic diary of respiratory symptoms

⁵ Same as #2

Patients who have had a recent COPD exacerbation (<12 weeks since discharge) accompanied with respiratory failure who meet the above inclusion criteria will be considered for participation in the study.

Once informed consent has been obtained patients will be given the opportunity to participate in the sleep substudy until the enrollment goal of ten subjects has been achieved. A separate protocol and consent form has been submitted for this study. The following procedures will be performed as part of the main study:

Outpatient HNHF-O2 Protocol

Version 3.0

10/06/2017

Test	Visit 1 Screening	Visit 1a Baseline	Visit 2 Clinic Placed on HNHF-O2	Visit 3 Phone Call Day 1	Visit 4 Phone call Day 3 ± 3	Visit 5 Clinic Day 7 ± 5	Visit 6 Phone call Day 17 ± 3	Visit 7 Clinic Day 28 ± 5	Visit 8 Phone call Day 37 ± 3	Visit 9 Clinic Day 49 ± 5	Visit 10 Phone call Day 58 ± 3	Visit 11 Clinic Day 70 ± 5	Visit 12 Phone call Day 80 ± 3	Visit 13 Clinic Day 90 ± 5
Screen	X													
Informed Consent	X													
History & Physical		X				X		X		X		X		X
Pregnancy test for women of childbearing potential		X												
Arterial blood gas◆		X	X											x
Pre- and Post- Bronchodilator Spirometry		X												X
6 minute walk distance		X												X
mMRC Questionnaire		X ²												
Borg Questionnaire		X ²	X			X		X		X		X		X
Assess Accessory Muscle use		X	X			X		X		X		X		X
Assess subject comfort		X	X			X		X		X		X		X

Outpatient HNHF-O2 Protocol

Version 3.0

10/06/2017

Test	Visit 1	Visit 1a	Visit 2	Visit 3	Visit 4	Visit 5	Visit 6	Visit 7	Visit 8	Visit 9	Visit 10	Visit 11	Visit 12	Visit 13

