At baseline, patients will have measurement of vital signs (heart rate, respiratory rate and blood pressure), dyspnea (modified Borg score, mMRC) arterial blood gas after 5 minutes of inspiring supplemental oxygen to keep $\text{SaO}_2 > 90\%$, and use of accessory muscles of ventilation. Patients will have spirometry performed pre-and post-bronchodilator administration. Patients will have assessment of their current respiratory health by completing CAT, mMRC and SGRQ questionnaires. A detailed history of their exacerbation frequency and severity will be obtained. Patients will perform a 6-minute walk test. Patients GOLD grade and group will be classified and patients BODE scores will be calculated.

Patients will be queried regarding the presence and magnitude of complaints of cough and sputum production by using a daily electronic diary for a 2-week period of run in. After the 2-week run-in period the patient will be scheduled to return to initiate HFNC with oxygen therapy.

Electronic daily diary of respiratory symptoms.

- ❖ Breathlessness (Modified Borg Scale)
- ❖ Sputum Quantity, Color, and Consistency
- ❖ Peak Flow Measurements
- ❖ Presence of Temperature Over 100°F
- ❖ Presence of Any Cough, Wheeze, Sore Throat or Nasal Congestion

Outpatient HNHF-O2 Protocol

Version 3.0

10/06/2017

Patients will be seen in clinic and instructed in the use of HNHF-O2 and its proposed benefits. The necessity of compliance and adherence to the treatment plan will be emphasized.

Following the outpatient clinic visit, patients will be set up at home using an established home vendor for respiratory equipment. Patients will continue to report their daily respiratory symptoms via the electronic diary.

Post placement on optimal dose of HNHF-O2 therapy, subjects will be called the next day to determine if there were any problems.

Patients will report to clinic at baseline and then 7 ± 2 , 28 ± 5 , 49 ± 5 , and 70 ± 5 days for the following assessment:

- Measurements of vital signs (heart rate, respiratory rate and blood pressure)
- Respiratory patient-discomfort and dyspnea assessed using an unmarked 100 mm visual analogic scale from “no discomfort” to “maximal imaginable discomfort”
- Likert scale model indicating marked improvement (+2), slight improvement (+1), no change (0), slight deterioration (-1) and marked deterioration (-2)

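### Spirometry, 6MWD and BODE baselines are taken before a 2-week run-in without the device, so the change described as 90 days of HNHF-O2 nominally covers about 104 days

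*Combined protocol and SAP*

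**What the plan says.** The study is an "open-labeled pilot study of thirty patients" with no comparator (section 1). Section 10(g) describes a baseline assessment with spirometry, 6-minute walk, CAT, mMRC, SGRQ, GOLD and BODE. Patients are then followed "using a daily electronic diary for a 2-week period of run in", and the next step is: "After the 2-week run-in period the patient will be scheduled to return to initiate HFNC with oxygen therapy".

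Footnote 2 to the study overview puts the tests and the diary set-up in one assessment: "spirometry, 6 MWT, questionnaires (CAT, SGRQ), set baseline diary for respiratory symptoms".

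In the schedule table, the rows "Pre- and Post- Bronchodilator Spirometry" and "6 minute walk distance", and those for SGRQ, BODE and CAT (labelled COPD Activity Test), are marked at Visit 1a and Visit 13 only. GOLD is marked at Visit 1a only, although the text of 10(g) also lists it at Day 90. Visit 2, where the device is placed, has ABG, Borg, accessory muscle use and comfort, but none of the functional tests.

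Sections 10(f) and 10(i) plan the analysis: "Changes in spirometry, 6MWD, GOLD grade and class and BODE scores prior to and after 90 days of HNHF-O2 will be analyzed". CAT and SGRQ share the timing of these measures, but no change analysis is stated for them.

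**The concern.** The analysis is described by the length of device use, but its starting value was measured before the device was available. Patients enter within 12 weeks of discharge after an exacerbation, so they may still be recovering during the run-in. With no control arm, nothing in the analysis removes that recovery. Any improvement in FEV1, walk distance or BODE over those two weeks would be counted in a change that a reader would take to be 90 days on HNHF-O2.

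ABG is a related case. It is scheduled at Visits 1a, 2 and 13. The protocol does not say which of the first two is the pre-treatment value, or whether the Visit 2 sample is drawn before first placement. This matters because baseline PaCO2 is to be examined as an influence on the change in PaCO2.

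**Working it through.** The documents give no effect size, SD or power for these changes, so there is no stated figure to reproduce. The check is one of timing.

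**Inputs**
- Run-in: 14 days (section 10(g)).
- Day count: from initiation of HNHF-O2. The telephone-call paragraph of 10(g) says so for the calls, and the schedule table numbers calls and clinic visits in one sequence. Day 90 therefore excludes the run-in.
- Final visit window: ±5 days in the schedule table, ±2 days in the text.
- Order of events: inferred from the text of 10(g) and overview footnote 2. Visit 1a has no day number.

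**Interval actually measured**

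Interval = run-in + days from device start to Visit 13. Off-device share of time = 14 / interval.

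| Visit 13 on day | Interval (days) | Off-device share |
|---|---|---|
| 85 | 99 | 14.1% |
| 88 | 102 | 13.7% |
| 90 | 104 | 13.5% |
| 92 | 106 | 13.2% |
| 95 | 109 | 12.8% |

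**If the gap is not exactly 14 days.** For a gap of g days the share is g / (g + 90). As assumed examples, g = 7 gives 7/97 = 7.2% and g = 21 gives 21/111 = 18.9%.

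**How much recovery could fall in the run-in.** The documents do not say, so these are assumptions. If recovery is linear, the share is 14/104 = 13.5%. If it is exponential with time constant τ, the share of the recovery between baseline and Day 90 that falls in the run-in is (1 − e^(−14/τ)) / (1 − e^(−104/τ)):
- τ = 56 days: 0.2212 / 0.8439 = 26%
- τ = 28 days: 0.3935 / 0.9756 = 40%
- τ = 14 days: 0.6321 / 0.9994 = 63%

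**What a Visit 2 baseline would leave.** The interval becomes 90 days (85 to 95 with ±5) and the off-device share becomes zero. The rest of the recovery stays in the change: about 87% (linear), 74% (τ = 56), 60% (τ = 28) or 37% (τ = 14).

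**The case against.** The best reply is that little depends on this. The primary endpoints are tolerance and hours of use, section 10(i) says the study is not an efficacy trial, and these changes carry no hypothesis or threshold. A value taken before the run-in is still a value prior to therapy, so the wording is imprecise about the interval without contradicting itself. The larger confounder is the single-arm design, which moving the baseline does not cure. All of this stands. It limits the weight of the point but does not remove the mismatch between the interval measured and the interval described.

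The timing is also inferred. The diary row is marked at Visit 1 as well as at 1a, so the run-in could begin before Visit 1a and the gap be shorter than 14 days. The text also uses baseline as the starting point for the on-device clinic visits. Footnote 2 favours the reading taken here, but the documents do not fix a 14-day minimum.

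A reader might infer more than the documents support:
- *That the run-in is untreated.* It is not. Supplemental oxygen is part of usual care under section 10(b), and usual maintenance medication continues under 10(g). Only the device is absent.
- *That about 13% of the observed change precedes therapy.* The 13.5% is a share of time. It becomes a share of recovery only if recovery is linear, and a share of the observed change only if there is also no device effect. If recovery and device effect were equal, for example, it would be 13.5% / 2 = 6.7% of the observed change.
- *That recovery during the run-in is established.* Entry soon after discharge makes it plausible, but the documents give no data on it.
- *That the protocol credits these changes to the device.* It says they will be analysed; it does not say to what they will be attributed.
- *That a pre-device baseline would isolate the device effect.* It removes only the run-in part.

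**Conclusion.** The point holds as a mismatch in the baseline of non-primary outcomes. Spirometry, 6MWD and BODE have no value at device start, and the change described as 90 days of HNHF-O2 nominally spans about 104 days (99 to 109 with the ±5 window), with 14 of them off the device. GOLD has the same baseline timing, but the table and text disagree on whether it is repeated at Day 90. CAT and SGRQ are affected only if their change is analysed.

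This rests on reading Visit 1a as the start of the run-in and on counting Day 90 from initiation. The size of any resulting bias cannot be given from the documents: the 13% to 63% range for recovery in the run-in depends wholly on assumed curves. The reason to act is that the two weeks before placement cannot contain a device effect and can be removed from the comparison at small cost.

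**What to change.** Take spirometry, 6-minute walk, CAT, SGRQ and GOLD/BODE scoring, with the assessments that feed those scores, at Visit 2 before the device is applied. Define the Visit 2 pre-device values as the baseline for all change scores. If the Visit 2 ABG is to be the pre-treatment reference, state that it is drawn before first placement. Set the order of the walk test relative to ABG, Borg and comfort. Mark GOLD at Visit 13 in the table so that it agrees with the text.

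The cost is an amendment to the schedule and text, a longer Visit 2 and a shorter Visit 1a. No tests are added, and no entry criterion uses the moved measures. The drawback is that patients lost during the run-in would have no functional baseline. Testing at both visits would avoid this, at the price of one extra set of tests per patient.

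If the tests stay at Visit 1a, date that visit relative to the run-in and report the result as change from baseline to Day 90, including about two weeks without the device. Under either option, state that recovery after device start cannot be separated from a device effect in this design, and do not attribute the change to the device.

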- Side effects related to high flow nasal administration: nasal dryness, epistaxis, nasal crusting, eye discomfort, pressure discomfort, increase rhinitis, decreased smell, post nasal drip, hoarseness
- Hours of daily use of HNHF-O2 therapy
- Daily record keeping of daily diary review

At day 90 ± 2 the following will be measured:

- Measurements of vital signs (heart rate, respiratory rate and blood pressure)
- Respiratory patient-discomfort and dyspnea assessed using an unmarked 100 mm visual analogic scale from “no discomfort” to “maximal imaginable discomfort”
- Likert scale model indicating marked improvement (+2), slight improvement (+1), no change (0), slight deterioration (-1) and marked deterioration (-2)
- Side effects related to high flow nasal administration: nasal dryness, epistaxis, nasal crusting, eye discomfort, pressure discomfort, increase rhinitis, decreased smell, post nasal drip, hoarseness
- Hours of daily use of HNHF-O2 therapy
- Daily record keeping of daily diary review
- Arterial blood gas on room air after the participant has been off the Airvo Device for 20 minutes.
- Pre-and post-bronchodilator spirometry

Outpatient HNHF-O2 Protocol

Version 3.0

10/06/2017

- CAT, SGRQ
- 6 Minute walk test
- GOLD grade and group will be classified
- BODE scores will be calculated.

Application of HNHF-O2 therapy. During HNHF-O2, oxygen will be passed through a heated humidifier (myAIRVO 2, Fisher and Paykel Healthcare) and applied continuously through large-bore binasal prongs, with a gas flow rate of 20-35 liters per minute (or as high as tolerated). Temperature will be adjusted based on patient's comfort and range from 34-37 degrees based on prior experience. The fraction of oxygen in the gas flowing in the system will be adjusted to maintain an SpO2 of 90% or more. High-flow oxygen will be applied at the highest tolerated flow up to 35 lpm at home. Meter time and patient's log of hours of daily use will be measured and compared.

Hypercapnic COPD patients are encouraged to use supplemental oxygen therapy on a continuous basis. The use of the humidified nasal high-flow device in this protocol is not expected to change the total number of hours that the patient receives supplemental oxygen; however it will change the manner in which the oxygen is delivered. Patients will be encouraged to use the device for oxygen delivery as many hours per day as possible.

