During the subject's hospitalization various medications including bronchodilators, corticosteroids, and antibiotics may be administered to manage the COPD exacerbation. These will be prescribed by the subject's physician as standard of care. The subject's usual maintenance medications will be prescribed as clinically indicated as standard of care. Other testing and procedures (such as laboratory testing and radiographic imaging) may be performed. These would also be standard of care.

myAIRVO 2 device. The myAIRVO 2 device is a humidifier with integrated flow generator that delivers high flow warmed and humidified respiratory gases to spontaneously breathing patients through a variety of patient interfaces. It is intended for the treatment of spontaneously breathing patients who would benefit from receiving high flow warmed and humidified respiratory gases. The myAIRVO 2 is for patients in homes and long-term care facilities. The flow may be from 2 – 60 L/min depending on the patient interface. There are few expected side effects of using the myAIRVO 2 device – if the humidification is too low, the subject may experience nasal/throat discomfort or epistaxis.

Optiflow+ nasal cannula. The Optiflow+ nasal cannula is a nasal cannula patient interface for delivery of humidified respiratory gases. There are few expected side effects of using the Optiflow+ nasal cannula – some minor irritation or sensitivity may occur where the cannula sits on the skin.

Telephone calls. Subjects will receive telephone calls on days 1, 3, 17, 37, 58, 80 (after initiation of HNHF-O2) to determine vital status, assess adverse events, compliance with the device, and to answer any questions they may have regarding the study. In addition to the scheduled telephone calls, the subject may receive phone calls from the monitors of the electronic daily diary if the subject fails to report symptoms for three consecutive days.

h) Data and Specimen Banking

Not applicable.

i) Data Management

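### The side-effect checklist does not ask about throat discomfort, a device effect the protocol itself expects, and no comparison of throat or nasal symptoms with the pre-device period is stated

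*Combined protocol and SAP*

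**What the plan says.** The protocol touches throat and nasal symptoms in four places.

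- **Checklist.** Section 10(g) prints the same side-effect list twice, once for the clinic visits up to day 70 and once for day 90: "nasal dryness, epistaxis, nasal crusting, eye discomfort, pressure discomfort, increase rhinitis, decreased smell, post nasal drip, hoarseness".
- **Expected device effects.** The device description in section 10(g) states that "if the humidification is too low, the subject may experience nasal/throat discomfort or epistaxis". Section 11 repeats the warning.
- **Diary.** One line of the daily electronic diary in section 10(g) reads "Presence of Any Cough, Wheeze, Sore Throat or Nasal Congestion". The run-in sentence says patients are asked about "complaints of cough and sputum production by using a daily electronic diary for a 2-week period of run in". After home set-up, "Patients will continue to report their daily respiratory symptoms via the electronic diary". Figure note 2 has staff "set baseline diary for respiratory symptoms", note 4 has them "review daily electronic diary of respiratory symptoms", and the visit lists include "Daily record keeping of daily diary review".
- **Analysis.** Sections 10(f) and 10(i), in identical text, put tolerance in the primary endpoint beside hours of use. They follow tolerance and side effects over time, per patient and as group trends, without naming a data source or a pre-device reference. The diary is named only as one of two sources for hours of use. The explicit before-and-after comparison at 90 days covers spirometry, walk distance, GOLD and BODE.

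**The concern.** The checklist is the only structured instrument aimed at effects of the high-flow device, and it leaves out an effect that the protocol predicts twice. A symptom that is prompted at every visit and one that must be volunteered are not counted on the same footing, so a side-effect table built from this checklist could not report throat discomfort beside the nasal items.

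The second part concerns the reference level. Sore throat and nasal congestion can come from the underlying disease or an infection as well as from the device. The study has no control arm, so the only comparison available is with the same patients before the device. The 2-week run-in is the only daily pre-device record. If symptoms are followed only once the device is in use, the report cannot say whether they were new. The stake is how well the tolerance result can be described, not whether the study can be run.

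**Working it through.** The plan gives no figure on this point, so the main check sets the texts side by side. The arithmetic after that is illustrative.

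**1. Expected effects against the checklist**

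| Effect named in sections 10(g) and 11 | Matching checklist item |
|---|---|
| Nasal discomfort | nasal dryness, nasal crusting, rhinitis |
| Epistaxis | epistaxis |
| Throat discomfort | none; nearest are hoarseness (a voice symptom) and post nasal drip |

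**2. Number of checklists.** On-device clinic visits fall on days 7, 28, 49, 70 and 90, so 30 patients × 5 visits = 150 checklists if all attend. If the checklist is also given at baseline, 30 × 6 = 180. The documents do not settle which. The sentence introducing the clinic assessments in section 10(g) puts baseline at the head of the visit days. Figure note 2 and the separate baseline paragraph do not mention side effects, figure note 4 does, and the schedule of tests has no row for the checklist.

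**3. What the run-in diary holds.** The run-in sentence names only cough and sputum. Figure note 2 sets up a baseline diary for respiratory symptoms, and patients later continue that reporting. The natural reading is that the full diary, including sore throat, runs from the start, but this is not explicit. Planned diary days are 30 × 14 = 420 in the run-in and 30 × 90 = 2,700 on the device.

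**4. Why a reference level matters (assumed rates).** Sore throat on 20% of on-device days is a rise of 20 − 5 = 15 points if the run-in level was 5%, and 20 − 20 = 0 if it was 20%.

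**5. Precision of a within-patient comparison (assumed SDs).** The 95% half-width of the mean change is t(0.975, n − 1) × SD / √n.

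| SD of change (points) | n = 30 | n = 24 (assumed diary losses) |
|---|---|---|
| 15 | ±5.6 | ±6.3 |
| 25 | ±9.3 | ±10.6 |
| 35 | ±13.1 | ±14.8 |

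At the largest SD the interval is nearly as wide as the 15-point example, so the result can only be descriptive.

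**6. One diary response or four.** If the shared diary line is a single yes/no, and the other three symptoms are present on a share c of days independently of sore throat, a 15-point rise in sore throat moves the composite by (1 − c) × 15. That is 7.5, 4.5 or 1.5 points for an assumed c of 0.5, 0.7 or 0.9. If the four symptoms are stored separately, there is no masking.

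**7. Patients who stop (assumed pattern).** Suppose 3 of 30 stop early with a 60-point rise and 27 continue with a 5-point rise. The mean over all patients is (3 × 60 + 27 × 5) / 30 = 10.5 points. Among the 27 who remain it is 5.0. Any comparison should therefore include those who stop.

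**The case against.** The best reply is that throat complaints have several other ways to reach the investigators. Sore throat is prompted in the daily diary and staff review that diary. Six scheduled calls ask about adverse events, and figure note 3 has staff ask about problems. Comfort is assessed at baseline, at device start and at each later clinic visit, and history and physical examination are repeated at the later clinic visits. Section 10(l) provides monthly monitoring and review of all adverse events, with special attention to patients who stop the device. All of this stands. A reader might infer from the checklist that throat symptoms go unrecorded; the documents do not support that. What these routes lack is a prompted device side-effect question on the same footing as the nine existing ones.

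Three other strong readings also fail.

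- A reader might say that the checklist ignores the throat altogether. Hoarseness and post nasal drip are close to it, so the gap is specifically throat discomfort or sore throat.
- A reader might say that nasal symptoms have no pre-device value. If the checklist is given at baseline, they have one; the text is unclear on this.
- A reader might say that the analysis rules out a run-in comparison. It does not. The group-trend clause is not tied to days of use, and the comparison is simply not stated.

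It is also fair to say that the diary and comfort forms are not in view, that the diary is presented as a respiratory symptom record and not as a tolerance instrument, and that a run-in comparison in a 30-patient pilot is an improvement rather than the repair of an error. That limits the weight of the second part. It does not remove the first, which is a mismatch within the protocol.

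**Conclusion.** The point holds and is minor. Both printed checklists omit throat discomfort although the protocol expects it, and neither analysis section states a comparison of throat or nasal symptoms with the period before the device. These two statements rest on the text alone. The count of 150 on-device checklists assumes 30 patients with full attendance; 180 depends on one reading of the baseline sentence.

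The symptom rates, SDs, masking shares and stopping pattern are assumptions chosen to show scale and are not evidence of a defect in this study. A reader might go further and conclude that the primary endpoint or the sample size is undermined. That is not supported: section 10(i) bases the sample size on withdrawal for intolerance, which is counted whether or not the checklist has a throat item. Nor would the added comparison establish that the device causes symptoms, because it cannot separate a device effect from recovery after the exacerbation or from infection.

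**What to change.** 1. Add *throat discomfort/sore throat* to both side-effect lists in section 10(g). State that the whole checklist is given once before the device is started, so that all ten items have a pre-device value and the baseline question is settled.
2. Confirm how the diary stores the shared symptom line. If it is one response, hold sore throat and nasal congestion (and, for consistency, cough and wheeze) as separate yes/no fields from the start of the run-in. If they are already separate, nothing changes.
3. Where separate fields exist, add to sections 10(f) and 10(i): *For each patient, the percentage of completed diary days with sore throat, and with nasal congestion, will be reported for the 2-week run-in and for all on-device days. Patients who stop the device are included with their days up to stopping. Mean within-patient changes with 95% intervals will be given descriptively beside the checklist results.*

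The cost is one extra question per visit, at most a small diary configuration change with up to three more taps a day for the patient, and one more table. No new visit, procedure or staff is needed.

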	Screening	Baseline	Clinic Placed on HNHF- O2	Phone Call Day 1	Phone call Day 3 ± 3	Clinic Day 7 ± 5	Phone call Day 17 ± 3	Clinic Day 28 ± 5	Phone call Day 37 ± 3	Clinic Day 49 ± 5	Phone call Day 58 ± 3	Clinic Day 70 ± 5	Phone call Day 80 ± 3	Clinic Day 90 ± 5
Epworth Sleepiness Scale	X													
Berlin Sleep Questionnaire	X													
STOP-Bang Questionnaire	X													
St. George's Respiratory Questionnaire		X												X
GOLD Category		x												
BODE Index		X												X
Daily Diary	X	X	X			X		X		X		X		X
COPD Activity Test		X												X
Review current medications	X	X	X	X	X	X	X	X	X	X	X	X	X	X
Phone call				X	X		X		X		X		X	
Sleep substudy participants														
Insomnia Severity index		X												
Home sleep study		X ¹				X						X		
Epworth Sleepiness		X ²				X ²						X ²		

Outpatient HNHF-O2 Protocol

Version 3.0

10/06/2017

Scale														
-------	--	--	--	--	--	--	--	--	--	--	--	--	--	--

¹ For those subjects enrolled in the sleep substudy the acquaintance and baseline sleep studies must be completed before beginning HNHF-O2

² Questionnaires are done at baseline visit and repeated at home prior to the baseline, day 7, and day 70 sleep studies.

◆ For ABGs, the test will be done on room air after the participant has been off the Airvo device for 20 minutes. If the participant starts to desaturate, then it can be done on 2L of oxygen.

Outpatient HNHF-O2 Protocol

Version 3.0

10/06/2017

There will be collection of demographic data including age, gender, race, current medications, and comorbid conditions. A patient history of duration of the nature and course of prehospital symptoms, past medical history of smoking, and past use of respiratory medications and nonpharmacological therapy for COPD will be elicited. Historical collection of available clinical data including exacerbation history, reports of chest imaging as well as pulmonary function and/or exercise or cardiac data will be collected.

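### The schedule and the Day 90 list omit mMRC, which the Day 90 BODE score presumably needs, and the schedule and text conflict on GOLD at Day 90

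*Combined protocol and SAP*

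**What the plan says.** Section 10 f) Study Endpoints, repeated in section 10 i) Data Management, states: "Changes in spirometry, 6MWD, GOLD grade and class and BODE scores prior to and after 90 days of HNHF-O2 will be analyzed".

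At baseline, section 10 g) says: "Patients will have assessment of their current respiratory health by completing CAT, mMRC and SGRQ questionnaires". The same paragraph then has GOLD classified and BODE calculated.

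The Day 90 list in section 10 g) asks for spirometry, the 6-minute walk, CAT and SGRQ. It also says "GOLD grade and group will be classified" and "BODE scores will be calculated". It does not name mMRC. Its dyspnea item is different: "Respiratory patient-discomfort and dyspnea assessed using an unmarked 100 mm visual analogic scale".

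In the schedule table, the rows "mMRC Questionnaire" and "GOLD Category" each carry one mark, at Visit 1a. The BODE row is marked at Visit 1a and at Visit 13 (Day 90).

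The overview figure has footnotes. Footnote 2 lists an assessment set that includes mMRC, spirometry, the walk test, CAT and SGRQ. Footnote 5 says only that its set is the same as that of footnote 2.

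**The concern.** A before-after comparison needs the same inputs at both times. At baseline mMRC is collected and BODE is then derived. At Day 90 BODE is to be derived again, but neither the visit list nor the schedule asks for mMRC.

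mMRC is the patient's own grading of dyspnea at the time of the visit. If it is not asked at Visit 13, it cannot be reconstructed from the chart. The patient's change in BODE is then missing, or rests on a substitute that the protocol does not define. Using the Borg score or the 100 mm scale at Day 90 would compare different dyspnea instruments at the two times.

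For GOLD, the question is whether staff at Visit 13 classify it (as the list says) or not (as the table implies).

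**Working it through.** No figure in the plan bears on this point, so the check is a side-by-side reading. The schedule has 14 visit columns: Visits 1, 1a, and 2 to 13. Visit 13 is the Day 90 clinic visit.

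| Item | Schedule, Visit 1a | Schedule, Visit 13 | Day 90 list | Footnote 5 (via footnote 2) |
|---|---|---|---|---|
| mMRC | marked | not marked | not named | included |
| GOLD | marked | not marked | named | not mentioned |
| BODE | marked | marked | named | not mentioned |
| Spirometry | marked | marked | named | included |
| 6-minute walk | marked | marked | named | included |
| SGRQ | marked | marked | named | included |

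1. **Is the gap a text-extraction fault?** Unlikely. Other rows of the same table (Borg, accessory muscle use, comfort, SGRQ, BODE) keep their Visit 13 marks, and the Day 90 list omits mMRC independently.

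2. **Which visit does footnote 5 describe?** The figure is not shown. The footnote 2 set includes spirometry, walk test and SGRQ, and in the schedule these recur together after baseline only at Visit 13. Day 90 is therefore the likely reading. On that reading the figure calls for mMRC at Day 90, while the table and list do not.

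3. **Does the superscript on the mMRC mark fill the gap?** The Visit 1a mark carries a superscript 2. If it refers to the table's own footnote 2, the repeats are tied to the baseline, day 7 and day 70 sleep studies, in a substudy with a goal of ten subjects. None is at Day 90. If it refers to the figure's footnote 2, it describes the baseline set and adds no Visit 13 mark.

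4. **Does BODE need mMRC?** The documents do not print BODE's components. The baseline text collects mMRC and then derives BODE, which fits mMRC being the dyspnea component but does not state it. This is an assumption.

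5. **GOLD.** The table has no Visit 13 mark, the list names it, and the endpoint paragraph analyzes its change. That is a conflict between table and text, not an omission. The inputs to GOLD are not printed either, so nothing here shows that it could not be classified at Day 90.

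**The case against.** The strongest reply is that the protocol probably intends mMRC at Day 90. Footnote 5 most likely says so, and the schedule asks for BODE at Visit 13, which could itself prompt staff to collect the input. The endpoints are also supporting ones: the primary endpoints are tolerance and hours of use, and section 10 i) says that this is not an efficacy trial. Dyspnea at Day 90 is measured in other ways too, by Borg at Visit 13, by the 100 mm scale in the Day 90 list, and by the breathlessness item in the daily diary.

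Most of this stands. It limits the point to one presumed component of one composite and to one table-text conflict; it does not put the evidence on dyspnea at risk. It does not remove the point, because an intention found only in a figure footnote is contradicted by the two places that set out what is done at the visit.

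A reader might go further and infer any of three things:

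- **That GOLD is not planned at Day 90.** The Day 90 list says that it is.
- **That baseline mMRC will be carried forward, so that dyspnea contributes no change to BODE.** No such rule appears; the protocol is silent on a missing BODE component.
- **That no patient will have a valid Day 90 BODE.** That requires every visit to follow the table or list literally, which the documents do not establish.

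**Conclusion.** The point holds in limited form. The schedule and the Day 90 list omit mMRC at Day 90, footnote 5 appears to include it, and BODE and its change from baseline are required. GOLD at Day 90 is a separate conflict between schedule and text.

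The size cannot be put as a number of patients, because it depends on which of the conflicting sources staff follow. What is exposed is the Day 90 side of the BODE comparison in a study planned to give evaluable data on 30 subjects, plus uncertainty over whether GOLD is reclassified. The primary feasibility endpoints are untouched.

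Two assumptions carry the conclusion: that BODE's dyspnea component is mMRC, and that footnote 5 labels the Day 90 visit. If the first fails, the three sources still disagree on whether mMRC is collected. If the second fails, mMRC is absent from Day 90 altogether and the gap is plainer. The correction is worth making before patients reach Visit 13, because a missed grade is lost for good.

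**What to change.** In the section 10 g) schedule, mark mMRC and GOLD category at Visit 13. In the Day 90 list, add mMRC beside CAT and SGRQ. Table, text and footnote 5 then agree, and the inputs match those collected at baseline.

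The cost is a schedule and text edit plus one questionnaire at a clinic visit already planned. The study procedures part of section 10 g) puts the time for the Borg and mMRC forms at one to two minutes. No treatment or clinical rule changes.
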